5.0 DOSE MODIFICATIONS FOR TOXICITIES

5.1 APL Differentiation Syndrome

The APL differentiation syndrome (described below) is a life-threatening complication of APL generally seen during Induction therapy after starting tretinoin and arsenic trioxide and prior to the patient achieving remission. Patients with high risk APL will receive dexamethasone at prophylaxis dosing to help prevent this syndrome. Also patients with standard risk APL who have their WBC count rise to $> 10,000/\mu\text{L}$ without symptoms of APL differentiation syndrome should begin prophylactic dosing of dexamethasone. If a patient develops symptoms of APL differentiation syndrome, follow guidelines for treatment dosing of dexamethasone (see below).

APL differentiation syndrome: a spectrum of clinical manifestations of a cardiorespiratory distress syndrome that include at least **three** of the following: respiratory distress, hypoxemia, fever, erythematous rash, pulmonary infiltrates, pleural or pericardial effusions, weight gain, peripheral edema, acute renal failure, congestive heart failure and hypotension. Patients with this syndrome may develop progressive cardiopulmonary failure.

If this syndrome is suspected:

- Promptly start treatment dose dexamethasone $5.8 \text{ mg}/\text{m}^2/\text{dose}$ IV BID (max $10 \text{ mg}/\text{dose}$ BID) for a minimum of 3 days and continue until resolution of symptoms, at which point dexamethasone should be continued at a prophylactic dose through Day 14.
- Hold tretinoin and arsenic trioxide. Once the symptoms and the patient's clinical condition improve, restart both medications at 50% of the previous dose (for tretinoin $6.25 \text{ mg}/\text{kg}/\text{dose}$ twice daily ($12.5 \text{ mg}/\text{m}^2/\text{day}$), for arsenic trioxide, $0.075 \text{ mg}/\text{kg}/\text{day}$) during the first 7 days. After 7 days, increase back to the full dose as prescribed in the protocol. Do not make-up missed doses during the cycle. If patients experience recurrent symptoms of APL differentiation syndrome, follow the same dose reduction directions above again and ensure the patient is on dexamethasone at treatment doses.

NOTE: In patients with high risk APL, Induction doses of IDArubicin should not be held or dose adjusted due to APL differentiation syndrome unless the clinician feels that cardiac function is impaired to a degree that would make idarubicin dosing contraindicated. If IDArubicin doses are held for this reason, the doses should be restarted when tolerable (do not skip idarubicin doses).

- Furosemide may be used as clinically indicated to treat fluid overload.
- Notify the study chair of any patient with persistent signs/symptoms of the APL differentiation syndrome that requires holding tretinoin and arsenic trioxide for more than 3 days.

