4.2.3 Induction Treatment Details – Standard Risk APL

ATRA should be started at the time of first suspicion of APL diagnosis and ATO given (when available) on Day 1 of protocol directed therapy.

Induction for standard risk APL consists of daily ATO and twice daily ATRA. Induction lasts at least 28 days (ATRA pre-treatment without ATO is not included in the 28 days). A bone marrow evaluation is performed on Day 29. Patients should remain on daily ATO/ATRA therapy while awaiting results of the Day 29 bone marrow hCR/hCRi assessment.

If hCR/hCRi is achieved per the Day 29 bone marrow, patients stop daily induction therapy and proceed to Consolidation. If hCR/hCRi is not achieved, patients continue with Induction up to a maximum of 70 days, and a bone marrow evaluation is done every 2 weeks until hCR/hCRi is achieved. This end Induction determination of hematologic complete response is not dependent on results of genetic testing (such as cytogenetics, FISH or RQ-PCR testing). Patients who appear not to have achieved hematological complete remission after Day 43 of Induction may benefit from consultation for a rapid pathology review beginning with the Day 57 marrow sample (See [Section 13](#) for details).

Induction ends with the confirmation of an hCR/hCRi and after a minimum of 28 days of induction. When hCR/hCRi is achieved the patient proceeds to Consolidation Cycle 1 (see [Section 4.3](#)). Following completion of Induction, Consolidation starts a minimum of 14 days from the end of Induction or when blood counts have recovered (ANC \geq 1,000/ μ L and platelets \geq 100,000/ μ L), whichever occurs later.

Tretinoin (ATRA): PO divided BID

Days: 1 - 28 minimum. Continue beyond Day 28 if not in hCR/hCRi up to a maximum of 70 days (See [Section 10.2](#) for response criteria and definition of hCR/hCRi).

Dose: 12.5 mg/m²/dose, twice daily. The total dose is 25 mg/m²/day divided twice daily.

Administer with food. Refer to [Appendix II](#) for dosing table (includes dose recommendations for very young patients). Guidance for administration of tretinoin by parents/caregivers can be found in [Appendix III](#).

Note: If the patient received pre-treatment with ATRA prior to starting Day 1 of protocol directed therapy (see [Section 3.2.3](#)), these pre-treatment doses are not considered part of the required 28 days minimum of induction protocol therapy.

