4.5.3 MRD Positive Consolidation Treatment Details – Standard Risk APL

MRD Positive Consolidation consists of a combination of high dose cytarabine, mitoxantrone and twice daily ATRA. This cycle lasts for 28 days. It is strongly recommended that the patients remain inpatient for the duration of this cycle of Consolidation and until count recovery.

Antifungal prophylaxis should be strongly considered (dependent on institutional practice) during this cycle due to an expected prolonged period of neutropenia. However, treating physicians should be aware that azole antifungal medications may increase ATRA toxicity due to inhibition of cytochrome P - 450 metabolism of ATRA. Thus patients should be monitored closely for adverse events such as, pseudotumor cerebri or renal dysfunction, during periods of concomitant use. For prophylactic antifungal use, initiation of an azole antifungal could be delayed until after completion of ATRA on Day 14 of this cycle or an alternate non-azole antifungal should be considered.

High Dose Cytarabine: IV over 1 - 3 hours every 12 hours

Days: 1 - 4 (8 total doses)

Dose: 1,000 mg/m²/dose every 12 hours. If BSA < 0.6 m², 33.3 mg/kg/dose.

NOTE: Administer steroid eye drops (0.1% dexamethasone or 1% prednisolone ophthalmic solution), 2 drops to each eye every 6 hours, beginning immediately before the first dose and continuing for 24 hours after the final dose. If patient does not tolerate steroid eye drops, may administer artificial tears on an every 2 - 4 hour schedule.

MitoXANtrone: IV daily over 15 - 30 minutes

Days: 3 - 6

Dose: 12 mg/m²/dose once daily. If BSA < 0.6 m² 0.4 mg/kg/dose.

Administer through the tubing of a rapidly infusing solution of D₅W or 0.9% NaCl. Avoid extravasation; the use of a central line is suggested. On Days 3 and 4, mitoxantrone should be given 8 hours after the 5th and 7th high dose cytarabine infusions are complete.

Tretinoin (ATRA): PO divided BID

Days: 1 - 14

Dose: 12.5 mg/m²/dose, twice daily. The total dose is 25 mg/m²/day divided twice daily.

Administer with food. Refer to [Appendix II](#) for dosing table (includes dose recommendations for very young patients).

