Note: If the patient received pre-treatment with ATRA prior to starting Day 1 of protocol directed therapy (see [Section 3.2.3](#)), these pre-treatment doses are NOT considered part of the required 28 days minimum of induction protocol therapy.

Arsenic Trioxide (ATO): IV daily over 2 hours (may lengthen infusion to 4 hours if active vasomotor symptoms occur)

Days: 1 - 28 minimum. Continue beyond day 28 if not in hCR/hCRi up to a maximum of 70 days (See [Section 10.2](#) for response criteria and definition of hCR/hCRi)

Dose: 0.15 mg/kg/day (no maximum dose)

IDArubicin: IV bolus over 15 minutes

Days: 1, 3, 5, 7

Dose: 12 mg/m²/dose, once a day

NOTE: if BSA < 0.6 m², 0.4 mg/kg/dose

Dexamethasone: PO/IV BID

Days: 1 - 14

Dose: 2.5 mg/m²/dose twice daily. The total daily dose is 5 mg/m²/day.

Note: This is prophylaxis dosing of dexamethasone. If the patient develops actual symptoms of differentiation syndrome, refer to [Section 5.1](#) for recommendations on diagnosis and management of differentiation syndrome including treatment dosing of dexamethasone.

Indications for intrathecal therapy

CNS Bleed

Patients with documented CNS bleed will receive CNS prophylaxis to include triple intrathecal chemotherapy at Day 29 of Induction. See table below for age-based dosing.

CNS Disease

Patients with CNS disease (see [Section 3.3.4](#) for definition) will receive twice weekly triple intrathecal chemotherapy (with a minimum interval of 48 hours between treatments) until the CSF is cleared plus two additional twice weekly treatments (minimum of 4 and maximum of 6 treatments). During Induction, patients with CNS disease will also receive a 10 mg/m² dose of leucovorin, 24 hours after each of the twice weekly triple intrathecal therapies.

Age-based dosing of triple intrathecal therapy:

Age	Triple Intrathecal Therapy (ITT)		
	Methotrexate	Hydrocortisone	Cytarabine
1 - 1.99 years	8 mg	15 mg	30 mg
2 - 2.99 years	10 mg	25 mg	50 mg
≥ 3 years	12 mg	35 mg	70 mg

See [Section 5.0](#) for Dose Modifications based on Toxicities.

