5.2 Tretinoin Dose Modifications (Including Modifications for Pseudotumor Cerebri)

Commonly observed toxicities with tretinoin include hepatotoxicity (increased AST and ALT), neurologic changes including headache or pseudotumor cerebri (see below), dermatology/skin changes and others including chelitis, epistaxis, fatigue, musculoskeletal pain, and conjunctivitis. If a patient experiences a Grade ≥ 3 toxicity that is felt to be related to tretinoin, then tretinoin will be held until the toxicity has resolved to the Grade 1 level.

At that time restart tretinoin at 25% dose reduction (19 mg/m²/day divided twice daily). Dosing of tretinoin should be as close as possible to 19 mg/m²/day divided twice daily, i.e., round to the nearest 10 mg (round < 5 mg down and ≥ 5 mg up). If necessary, the AM dose may differ from the PM dose to deliver a total daily dose as close as possible to 19 mg/m²/day divided twice daily. Recurrent episodes of Grade ≥ 3 toxicity will result in discontinuation of the tretinoin until the toxicity resolves to Grade ≤ 1; tretinoin will then be resumed with an additional 25% reduction (50% total dose reduction) in the tretinoin dose (12.5 mg/m²/day divided twice daily). Dosing of tretinoin should be as close as possible to 12.5 mg/m²/day divided twice daily; i.e., round to the nearest 10 mg (round < 5 mg down and ≥ 5 mg up). If necessary, the AM dose may differ from the PM dose to deliver a total daily dose closest to 12.5 mg/m²/day divided twice daily. Patients experiencing Grade ≥ 3 toxicity attributable to tretinoin while on 12.5 mg/m²/day of tretinoin should have tretinoin held until the toxicity resolves to Grade ≤ 1. tretinoin will then be resumed at the same 50% dose reduction (12.5 mg/m²/day divided twice daily) while continuing to monitor for toxicity and holding doses as needed for Grade ≥ 3 toxicity. Please notify the study chair about patients experiencing Grade ≥ 3 toxicity while on 50% dose reduction.

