If patients whose doses are reduced by 25% (19 mg/m²/day divided twice daily) or 50% (12.5 mg/m²/day divided twice daily) tolerate the lower dose for 7 days without recurrence of the toxicity that led to dose adjustment, a dose escalation may be attempted. If the patient had been decreased to 50% dosing (12.5 mg/m²/day divided twice daily) and tolerates an escalation to 75% dosing (19 mg/m²/day divided twice daily) for an additional 7 days, another escalation back to 100% dosing (25 mg/m²/day divided twice daily) may be attempted.

The APL Differentiation Syndrome should be treated as outlined in [Section 5.1](#).

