5.2.1 Pseudotumor Cerebri

Pseudotumor cerebri (PTC) must be confirmed by proper history, exam and other clinically relevant studies. Symptoms/signs of PTC include headache, papilledema, visual field defects (ocular/visual), and absence of focal neurological symptoms, except for occasional cranial nerve (CN) VI palsy (neuropathy: cranial CN VI). Cerebrospinal fluid should be evaluated and should be negative for signs of infection. However, lumbar puncture should be avoided while active coagulopathy is present. An opening pressure should be obtained; a pressure > 200 mm water helps to establish the diagnosis of PTC. A CT or MRI of the brain (to evaluate for meningitis, intracranial bleed, intracranial thrombosis, etc.) should be performed and should be compatible with PTC. Neurological and ophthalmologic consultations should be obtained in order to assist in making the proper diagnosis. Carefully follow the visual field status of the patient. One should also strongly consider obtaining a MRI/MRV to exclude the possibility of a sagittal sinus thrombosis. Consider acetazolamide (Diamox) therapy and periodic lumbar puncture with therapeutic removal of cerebrospinal fluid as appropriate for age/size.

If PTC develops:

- Hold tretinoin until this toxicity improves to Grade 0 or 1 (“mild” headache).

- Restart tretinoin at 75% of the original dose (19 mg/m²/day divided twice daily). If PTC reoccurs, hold tretinoin as above and then resume at 50% of original dose (12.5 mg/m²/day divided twice daily).

If the patient tolerates reduced dosing for more than 7 days, dose re-escalation can be attempted. Dose escalation from 50% (12.5 mg/m²/day divided twice daily) to 75% (19 mg/m²/day divided twice daily) to 100% (25 mg/m²/day divided twice daily) at 7 day intervals may be attempted if clinically appropriate.

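### Section 5.1 gives the tretinoin restart dose after differentiation syndrome in mg/kg; it should be 6.25 mg/m² per dose

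*Combined protocol and SAP*

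**What the plan says.** Section 5.1 covers suspected differentiation syndrome. Both differentiating agents are held, and once the patient improves the site is to "restart both medications at 50% of the previous dose (for tretinoin". The bracket then spells out the amounts. For tretinoin it reads "for tretinoin $6.25 \text{ mg}/\text{kg}/\text{dose}$ twice daily", followed by a daily total of 12.5 mg/m². For arsenic trioxide it gives 0.075 mg/kg/day. The reduced doses apply for the first 7 days, after which both drugs return to full dose.

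The full tretinoin dose is set in Section 4.2.3: "Dose: 12.5 mg/m²/dose, twice daily. The total dose is 25 mg/m²/day divided twice daily". Section 4.8.3 gives the same dose for high risk patients. Two other places define a 50% level for this drug. Section 5.2 resumes treatment after recurrent toxicity "with an additional 25% reduction (50% total dose reduction) in the tretinoin dose (12.5 mg/m²/day divided twice daily"), and Section 5.2.1 says to "resume at 50% of original dose (12.5 mg/m²/day divided twice daily") after recurrent pseudotumor cerebri. Appendix II doses tretinoin by body surface area throughout.

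**The concern.** One bracket states the same dose in two units that cannot both apply: 6.25 mg/kg twice daily is 12.5 mg/kg/day, not 12.5 mg/m²/day. Nowhere else does the protocol dose tretinoin by weight. The drug dosed by weight in that bracket is arsenic trioxide.

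The line is an operative instruction for children recovering from a syndrome that can kill, and it governs the restart of one of the drugs that cause it. Sections 4.1.2.1, 4.2.3.1 and 4.8.3 refer sites to Section 5.1 for management. Section 5.2 closes its own tretinoin rules by deferring to it: "The APL Differentiation Syndrome should be treated as outlined in" Section 5.1. Appendix II tabulates only the full dose of 25 mg/m²/day, so a site has to calculate the half dose, and the printed per-dose figure is the natural one to use. Taken literally, it turns an intended halving into a large overdose.

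**Working it through.** **Inputs**

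- Full tretinoin dose: 12.5 mg/m² per dose, twice daily (Sections 4.2.3 and 4.8.3).
- Restart fraction: 50% for both drugs (Section 5.1).
- Full arsenic trioxide dose: 0.15 mg/kg/day (Section 4.2.3).
- Largest full daily tretinoin dose in Appendix II: 40 mg twice daily, the last row of the table.

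**Reproducing the plan's figures**

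- Tretinoin per dose: 0.5 × 12.5 mg/m² = 6.25 mg/m².
- Tretinoin per day: 2 × 6.25 mg/m² = 12.5 mg/m².
- Arsenic trioxide: 0.5 × 0.15 mg/kg/day = 0.075 mg/kg/day.

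The number 6.25, the daily total of 12.5 mg/m² and the arsenic trioxide dose all reproduce. The 12.5 mg/m²/day total also equals the 50% level in Sections 5.2 and 5.2.1. Only the unit mg/kg on the tretinoin per-dose figure does not reproduce.

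**What the literal reading would give**

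Let W be weight in kg and S be surface area in m².

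- Literal daily dose: 2 × 6.25 × W = 12.5 × W mg.
- Intended daily dose: 12.5 × S mg.
- Ratio of literal to intended: W/S.
- Ratio of literal to full dose: 12.5 × W / (25 × S) = W/(2S).

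The literal dose exceeds the full dose whenever W/S is above 2 kg/m². Every body size assumed below is at least ten times that threshold.

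A comparison that needs no assumed body size: the last row of Appendix II is 2 × 40 = 80 mg/day, and 80 / 12.5 = 6.4 kg. Above 6.4 kg, the literal dose is larger than any full daily dose in the table. Eligible patients are at least 12 months old.

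**Size of the ratio**

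The protocol gives no body sizes, so the rows below are assumptions and not bounds.

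| Assumed size | Literal / intended (W/S) | Literal / full (W/2S) |
|---|---|---|
| 10 kg, 0.49 m² | 20.4 | 10.2 |
| 30 kg, 1.05 m² | 28.6 | 14.3 |
| 70 kg, 1.85 m² | 37.8 | 18.9 |
| 100 kg, 2.2 m² | 45.5 | 22.7 |

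The protocol's small-child dosing rules for other drugs imply a similar magnitude. Idarubicin is 12 mg/m², with "NOTE: if BSA < 0.6 m², 0.4 mg/kg/dose", so 12 / 0.4 = 30 kg/m². High dose cytarabine is 1,000 mg/m², and "If BSA < 0.6 m², 33.3 mg/kg/dose" gives 1,000 / 33.3 = 30.03 kg/m². At 30 kg/m², 6.25 mg/kg corresponds to 187.5 mg/m² per dose, which is 187.5 / 6.25 = 30 times the intended dose and 187.5 / 12.5 = 15 times the full dose.

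**The case against.** The strongest reply is that the sentence largely corrects itself. Its operative content is the 50% reduction, and a prescriber who knows the previous dose needs neither bracketed number. The correct daily total stands next to the wrong one, and every other tretinoin dose in the protocol is per m². The route to harm is also hard to picture. For the assumed child of 30 kg and 1.05 m², the literal reading is 375 mg/day, against 30 mg/day in Appendix II as the full dose. That is 12.5 times the full dose, in 10 mg steps of oral capsules, ordered as a reduction. A pharmacist would very likely stop it. This stands, and it limits the seriousness of the point, but a dosing line should not depend on someone downstream catching it.

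The fold figures are also open to challenge. The 30 kg/m² factor is a dosing rule for other drugs below 0.6 m², not a measured ratio, and the assumed 10 kg child gives about 20. Section 5.2 rounds the 50% level to the nearest 10 mg. If that rule carried over to Section 5.1, which does not say so, the intended dose for the 10 kg child would go from 0.49 × 12.5 = 6.1 mg to 10 mg/day, and the ratio would become 125 / 10 = 12.5. For the 30 kg child, 13.1 mg would become 10 mg/day and the ratio 37.5. The exact multiples are therefore soft. The conclusion that the literal dose is well above the full dose is not.

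Finally, the text was read from PDF by a program, so a misread unit cannot be fully excluded. It is unlikely, because the m² units for dexamethasone and for the tretinoin daily total in the same section came through correctly.

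**Conclusion.** The concern holds. The tretinoin restart dose in Section 5.1 carries the wrong unit; the protocol's own half dose is 6.25 mg/m² twice daily. That conclusion rests only on figures in the protocol and needs no assumption beyond the text having been read correctly. The size of a literal misreading does depend on body size: about 20 to 45 times the intended dose for the assumed sizes before any rounding, and above every full dose in Appendix II once weight exceeds 6.4 kg.

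This should be fixed because the line is an active safety instruction. It has no bearing on event-free survival, the sample size or the analysis, and nothing here suggests that any patient was misdosed.

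**What to change.** In Section 5.1, change the tretinoin per-dose unit from mg/kg to mg/m², so that the restart dose is 6.25 mg/m² per dose twice daily (12.5 mg/m²/day). Leave the arsenic trioxide figure of 0.075 mg/kg/day as it is. Check the line against the source page first, then send sites a short notice. The cost is a one-unit correction in an amendment plus that notice, with no change to design, sample size or analysis.

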5.2 Tretinoin Dose Modifications (Including Modifications for Pseudotumor Cerebri)

Commonly observed toxicities with tretinoin include hepatotoxicity (increased AST and ALT), neurologic changes including headache or pseudotumor cerebri (see below), dermatology/skin changes and others including chelitis, epistaxis, fatigue, musculoskeletal pain, and conjunctivitis. If a patient experiences a Grade ≥ 3 toxicity that is felt to be related to tretinoin, then tretinoin will be held until the toxicity has resolved to the Grade 1 level.

At that time restart tretinoin at 25% dose reduction (19 mg/m²/day divided twice daily). Dosing of tretinoin should be as close as possible to 19 mg/m²/day divided twice daily, i.e., round to the nearest 10 mg (round < 5 mg down and ≥ 5 mg up). If necessary, the AM dose may differ from the PM dose to deliver a total daily dose as close as possible to 19 mg/m²/day divided twice daily. Recurrent episodes of Grade ≥ 3 toxicity will result in discontinuation of the tretinoin until the toxicity resolves to Grade ≤ 1; tretinoin will then be resumed with an additional 25% reduction (50% total dose reduction) in the tretinoin dose (12.5 mg/m²/day divided twice daily). Dosing of tretinoin should be as close as possible to 12.5 mg/m²/day divided twice daily; i.e., round to the nearest 10 mg (round < 5 mg down and ≥ 5 mg up). If necessary, the AM dose may differ from the PM dose to deliver a total daily dose closest to 12.5 mg/m²/day divided twice daily. Patients experiencing Grade ≥ 3 toxicity attributable to tretinoin while on 12.5 mg/m²/day of tretinoin should have tretinoin held until the toxicity resolves to Grade ≤ 1. tretinoin will then be resumed at the same 50% dose reduction (12.5 mg/m²/day divided twice daily) while continuing to monitor for toxicity and holding doses as needed for Grade ≥ 3 toxicity. Please notify the study chair about patients experiencing Grade ≥ 3 toxicity while on 50% dose reduction.

If patients whose doses are reduced by 25% (19 mg/m²/day divided twice daily) or 50% (12.5 mg/m²/day divided twice daily) tolerate the lower dose for 7 days without recurrence of the toxicity that led to dose adjustment, a dose escalation may be attempted. If the patient had been decreased to 50% dosing (12.5 mg/m²/day divided twice daily) and tolerates an escalation to 75% dosing (19 mg/m²/day divided twice daily) for an additional 7 days, another escalation back to 100% dosing (25 mg/m²/day divided twice daily) may be attempted.

The APL Differentiation Syndrome should be treated as outlined in [Section 5.1](#).

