APPENDIX II: TRETINOIN (ALL-TRANS RETINOIC ACID, ATRA) DOSING TABLE

Dose: 25 mg/m²/day	
BSA (m²)	Dose
≤ 0.59	10 mg every day
0.6 - 0.99	10 mg twice daily
1 - 1.39	20 mg every AM, 10 mg every PM
1.4 - 1.79	20 mg twice daily
1.8 - 2.19	30 mg every AM, 20 mg every PM
2.2 - 2.59	30 mg twice daily
2.6 - 2.99	40 mg every AM, 30 mg every PM
3 - 3.39	40 mg twice daily

For additional administration guidelines for administering tretinoin (ATRA) to patients unable to swallow whole capsules either due to young age or level of consciousness (including intubated patients) please see [Appendix III](#). Further details about tretinoin (ATRA) can also be found in the commercial agent monographs manual titled “Drug Information for Commercial Agents used by the Children’s Oncology Group.” This manual is provided under Standard Sections for Protocols at:

https://www.cogmembers.org/site/pages/default.aspx?page=Prot_reference_materials .

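### Section 5.2's nearest-10-mg rounding does not guarantee a lower tretinoin dose: in two BSA bands the 25% first step equals the dose that was held

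*Combined protocol and SAP*

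**What the plan says.** Section 5.2 holds tretinoin for a related Grade 3 or higher toxicity until it resolves to Grade 1, then instructs sites to "restart tretinoin at 25% dose reduction (19 mg/m²/day divided twice daily". The rounding rule is "Dosing of tretinoin should be as close as possible to 19 mg/m²/day divided twice daily, i.e., round to the nearest 10 mg", with remainders of 5 mg or more going up. Morning and evening doses may differ "to deliver a total daily dose as close as possible to 19 mg/m²/day divided twice daily", so the rounding applies to the daily total.

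On recurrence, after a further hold, "tretinoin will then be resumed with an additional 25% reduction (50% total dose reduction) in the tretinoin dose", to 12.5 mg/m²/day with the same rounding. For patients on either reduced level who "tolerate the lower dose for 7 days without recurrence of the toxicity that led to dose adjustment, a dose escalation may be attempted"; a child at 50% moves to 75% for a further 7 days before 100%. The chair-notice sentence in this section concerns only the last level: "Please notify the study chair about patients experiencing Grade ≥ 3 toxicity while on 50% dose reduction".

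Appendix II gives the full dose as "10 mg twice daily" at 0.6-0.99 m² and "20 mg every AM, 10 mg every PM" at 1-1.39 m². It has no columns for reduced doses. Section 5.2.1 (pseudotumor cerebri) uses the same 19 and 12.5 mg/m²/day levels but does not repeat the rounding sentence.

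**The concern.** The section describes the first step as a reduction and later refers to it as the lower dose. With 10 mg units and small children, nearest-unit rounding can return the dose the child was already taking. A site following the text exactly would then restart at the same milligram dose that had been held for a Grade 3 or higher toxicity. The staged recovery would also lose its middle stage. What is at stake is the safety of individual children, not the trial's inference.

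**Working it through.** **Inputs.** Full rate 25 mg/m²/day and the dose bands (Appendix II); first step 19 and second step 12.5 mg/m²/day; nearest 10 mg on the daily total, 5 mg or more up (all Section 5.2).

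**Reproducing the plan's own figures.** 25 × BSA, rounded by this rule at every 0.01 m² from 0.20 to 3.39 m², matches every Appendix II row with no mismatch. Also 0.75 × 25 = 18.75, which the protocol gives as 19, and 0.50 × 25 = 12.5. The stated figures are sound.

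**First step.** Dose = 19 × BSA, rounded.
- 19 × 0.78 = 14.82 → 10 mg; 19 × 0.79 = 15.01 → 20 mg; 19 × 0.99 = 18.81 → 20 mg.
- 19 × 1.31 = 24.89 → 20 mg; 19 × 1.32 = 25.08 → 30 mg; 19 × 1.39 = 26.41 → 30 mg.

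**Second step.** Dose = 12.5 × BSA, rounded. For example, 12.5 × 0.99 = 12.4 → 10 mg and 12.5 × 1.32 = 16.5 → 20 mg.

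| BSA (m²) | Full (mg/day) | First step | Second step |
|---|---|---|---|
| 0.40-0.59 | 10 | 10 | 10 |
| 0.60-0.78 | 20 | 10 | 10 |
| **0.79-0.99** | **20** | **20** | 10 |
| 1.00-1.19 | 30 | 20 | 10 |
| 1.20-1.31 | 30 | 20 | 20 |
| **1.32-1.39** | **30** | **30** | 20 |
| 1.40-1.79 | 40 | 30 | 20 |

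From 1.40 m² up, the three levels are distinct at every point.

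**Size in the two null bands.** 20/0.79 = 25.3 and 20/0.99 = 20.2 mg/m²/day, which is 33% falling to 6% above 19. 30/1.32 = 22.7 and 30/1.39 = 21.6 mg/m²/day, which is 20% falling to 14% above 19.

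**Re-escalation, 50% → 75% → 100%.** At 0.79-0.99 m² it runs 10 → 20 → 20 mg; at 1.32-1.39 m² it runs 20 → 30 → 30 mg. The nominal 75% week is full dose.

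**Below 0.60 m².** The dose also stays at 10 mg, but no lower non-zero daily total exists on a 10 mg grid. At 0.53-0.59 m², 10 mg is already 18.9-16.9 mg/m²/day, at or below the target.

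**Sensitivity.** Using 18.75 in place of 19 moves the null bands only to 0.80-0.99 and 1.34-1.39 m². Rounding each 9.5 mg/m² dose separately would give 0.60-0.99 and 1.58-1.79 m² instead, but the text on unequal doses and the daily total, together with the Appendix II match, supports rounding the daily total.

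**The case against.** The strongest reply is that the rule does what it says. In both null bands the unchanged dose is the 10 mg step nearest to 19 mg/m²/day. At 0.79-0.99 m² the only lower fixed daily dose is 10 mg (12.7-10.1 mg/m²/day), which is the 50% step. Appendix II tolerates similar departures at full dose: 20 mg at 0.60 m² is 33.3 mg/m²/day (33% above 25) and 30 mg at 1.00 m² is 30 (20% above). All of this stands. It means that no stated number is wrong and that capsule size is much of the cause. It does not answer the point that a rule aimed only at closeness can undo a step whose stated purpose is to reduce the dose.

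The reply that harm is limited also stands. Tretinoin is first held to Grade 1. Recurrence brings another hold and a real cut in both null bands (20 → 10, 30 → 20). Section 8.1 allows removal for unacceptable toxicity or on the physician's judgment. Section 5.2 itself allows re-escalation after 7 tolerated days, so a null first step amounts to an earlier full-dose rechallenge.

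A reader might infer that recurrences would go unseen because the chair notice in Section 5.2 is tied to the 50% level. The documents do not support that: Section 11.4 requires reporting of all Grade 3 and higher non-hematological adverse events on therapy. What is not flagged is the unchanged dose itself.

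**Conclusion.** The point holds as a minor defect. The rounding rule does not guarantee a reduction. The first step is null at 0.79-0.99 and 1.32-1.39 m², and the second step repeats the first at 0.60-0.78 and 1.20-1.31 m². This rests on rounding the daily total, which the text supports.

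Three stronger readings are not supported. First, a reader might conclude that 19, 12.5 or the Appendix II table is miscalculated; each reproduces. Second, a reader might extend the finding to pseudotumor cerebri as a stated fault. Section 5.2.1 shares the dose levels but not the rounding sentence, so carry-over is an inference. Third, a reader might look for an effect on the primary result. This is a dose-modification rule that enters neither the EFS definition nor the power calculations. The documents give no BSA distribution, so the number of children affected cannot be computed.

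**What to change.** Add 75% and 50% dose columns by BSA to Appendix II and cite them from Sections 5.2 and 5.2.1. Section 5.4.1 already tabulates reduced idarubicin and mitoxantrone doses by BSA group. State that, where rounding reproduces the held dose and a lower dose exists, the restart must be lower. The choices below are clinical and belong to the sponsor; alternate-day tretinoin appears nowhere in the documents.

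- **1.32-1.39 m², first step:** 20 mg/day (15.2-14.4 mg/m²/day, equal to the second step), or alternate 30 and 20 mg days (mean 25 mg, 18.9-18.0 mg/m²/day, the nearest to 19 across the band).
- **0.79-0.99 m², first step:** alternate 20 and 10 mg days (mean 15 mg, 19.0-15.2 mg/m²/day), or 10 mg/day (equal to the second step). The alternating mean is nearer to 19 than 20 mg/day only up to 17.5/19 = 0.92 m²; above that, closeness is traded for a real reduction.
- **1.20-1.31 m², second step:** a lower dose exists, so the same clause applies. For example, alternating 20 and 10 mg days gives 15/1.20 = 12.5 to 15/1.31 = 11.5 mg/m²/day.
- **0.60-0.78 m², second step:** 10 mg/day is already the lowest fixed daily dose. The table should show that the two levels coincide.
- **Below 0.60 m²:** no lower dose exists; resume 10 mg/day and notify the study chair.

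The cost is one dosing-table amendment, with no extra patients, visits or tests. The downside is more complex dosing for families and sites, and a delivered dose somewhat below 19 mg/m²/day. With alternate-day dosing the shortfall is up to 20% at 0.79-0.99 m² (15.2 against 19) and up to 5% at 1.32-1.39 m² (18.0 against 19). It is larger with the flat doses.
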